4.1.5 Sensitivity analysis

Sensitivity analyses where missing data is handled in different ways will be carried out for the primary endpoint. To examine the impact of missing data, including the impact of non-responder imputation due to permanent discontinuation of IP, tipping point analyses will be performed for endpoints specified in Section 4.2. These analyses will vary the assumptions about outcomes among the subsets on the treatment arms that discontinue IP early. Details of the sensitivity analyses are provided in Section 4.2 with each associated endpoint.

4.1.6 Examination of model assumptions

Underlying model assumptions for all statistical models will be checked with graphical displays (e.g. plots of residuals versus predicted values, histograms with normal density overlaid, quartile-quartile [Q-Q] plots showing the residual quantiles versus quantiles of a normal distribution) as appropriate. If any model assumptions are not met, appropriate (or alternative) data transformations or the use of non-parametric approaches will be discussed as soon as is appropriate. The decision about an appropriate approach will be made before unblinding the data.

4.1.7

CCI

[REDACTED]

[REDACTED]

[REDACTED]

4.2 Analysis methods

4.2.1 Analysis of the primary variable

The primary estimand is evaluating the efficacy on disease activity of the pooled anifrolumab groups relative to placebo in subjects with active proliferative LN. This is measured by the

relative difference in change from baseline to Week 52 in the 24-hour UPCR. The full analysis set (as defined in Section 2.1.2) will be used, and any data collected after IP discontinuation will be excluded from the analysis, in order to reflect the effect of the initially assigned and dosed IP (anifrolumab or placebo), prior to the occurrence of the intercurrent event of IP discontinuation, applying a “while on treatment” estimand strategy. The individual anifrolumab regimens will also be assessed but not as part of the primary analysis.

The estimand for all continuous endpoints (including the primary endpoint) follows the “while on treatment” strategy, which includes data only up to IP discontinuation. If IP has not been reported as prematurely discontinued, available data up to and including Week 104 will be used for continuous endpoints analyses. Otherwise, the date of IP discontinuation will be determined as the date of last IP administration. However, all subjects who have an infusion of IP within the Week 48 analysis visit window will be determined to have completed treatment in the double-blind treatment period, and their Week 52 data will be included in the analyses.

The primary analysis will be performed using an MMRM fitted to log-transformed data comparing the pooled anifrolumab group with the placebo group, with fixed effects for treatment group, visit, stratification factors and log-transformed 24-hour UPCR at baseline. An interaction term for visit and treatment will also be included in the model to allow the relationship to differ across treatment groups. Note that visit will be fitted as a repeated variable in the model. Denominator degrees of freedom will be estimated using the Kenward-Roger approximation. An unstructured correlation pattern will be used to estimate the variance-covariance of the within-subject repeated measures. In the case that the model does not converge using an unstructured covariance matrix, the heterogeneous Toeplitz covariance structure will be evaluated, followed by the heterogeneous autoregressive of first order, heterogeneous compound symmetry, and homogeneous compound symmetry covariance structures in the case of further non-convergence. The restricted maximum likelihood method will be used.

Separate MMRMs will be fitted to all data from baseline to Week 52 for the analyses of Week 12 to Week 52, and to all data from baseline to Week 104 for the analyses of Week 64 to Week 104.

Stratification factors are:

- Results of IFN test at screening using a 4-gene type I IFN test (high versus low)
- 24-hour UPCR ≤ 3.0 mg/mg versus > 3.0 mg/mg (based on 24-hour UPCR performed on a sample obtained within 14 days prior to the expected date of randomisation). Without the results of the second (stratification) sample, subjects cannot be randomised. Turn-around time for results from central laboratory is up to 7 days. On rare occasion an extension of 30-day screening window is allowed if re-collection of the sample is necessary or the results needed for randomisation are delayed.

The 24-hour UPCR values will be log-transformed before analysis and the results will be back-transformed for presentation. Model assumptions will be checked as defined in Section 4.1.6. The estimated treatment effect, corresponding 95% CI, and two-sided unadjusted

p-value for the difference at Week 52 and nominal p-values for the difference at all other post-baseline visits will be presented.

The following sensitivity analyses will also be performed to assess the robustness of the primary analysis:

- Treatment policy analysis: Includes all data collected, irrespective of whether a subject discontinued IP.
- Biopsy analysis: Excludes any subjects whose adjudicated kidney biopsy results show them to be ineligible for study entry (i.e. subjects whose adjudicated kidney biopsy results are not class III or class IV)

Subgroup analyses will be performed as described in Section 4.3.

Summary statistics for 24-hour UPCR and change from baseline will be presented by week. Longitudinal presentations of results over time (i.e. for each post-baseline visit up to Week 104 where 24-hour UPCR is recorded) based on the same main analysis, with the corresponding 95% CI, will be created. Mean changes from baseline for 24-hour UPCR will be displayed in a longitudinal plot by treatment group only for the first year, where the estimated adjusted means with corresponding 95% CI at each visit will be displayed. A Kaplan-Meier plot will also be produced for time to 24-hour UPCR ≤ 0.7 mg/mg by treatment group for the whole study.

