5.1 Efficacy assessments

Efficacy measurements will be made at the times indicated in the Study Plan (for assessments to be performed at Screening and treatment period, see [Table 2](#) and [Table 4](#), respectively, and for those at Follow-up, see [Table 3](#) and [Table 5](#)).

The efficacy assessments based on laboratory tests include:

- Urine protein to creatinine ratio: This consists of:
 - **24-hour UPCr**: The 24-hour UPCr will be determined on a 24-hour UPCr sample.

This will be performed twice during the screening period, Weeks 0, 12, 24, 36, 52, 64, 76, 88, and 104 and at Early Discontinuation visit.

During the screening period two samples will be required:

- Screening sample at the start of the screening process, after the ICF is signed and
- Stratification sample within 14 days prior to the expected day of randomisation. Without the results of the second (stratification) sample, subjects cannot be randomised. Turn-around time for results from central laboratory is up to 7 days.

Starting from Week 0, the 24-hour UPCR sample must always be collected before the administration of IP. The sample collected at Week 0 (Day 1) will be the baseline sample which must be provided on Day 1 prior to randomisation and administration of first dose of IP.

The collection of the 24-hour UPCR sample should start preferably in the morning of the day before the scheduled visit and end in the morning of the day of the visit. The urine collection can be done within 1 day prior to the visit if the urine sample can be kept refrigerated until the day of the visit. The sample should be kept refrigerated whenever possible. If refrigeration is not possible, subjects should select the coolest possible place to store their urine sample, eg, a cool room or use a portable cooler with ice/ice pack.

In case subject has a medical reason which would impact the validity of the assessment of proteinuria (eg, urinary tract infection, heavy menstruation), or the sample was not collected appropriately, the collection of the sample may be done/repeated as follows:

- Screening samples: As soon as possible before the next scheduled sampling is due
- Week 0: Prior to IP administration (which may require the Visit 1 to be postponed)

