8.5.1 Analysis of the primary variable

The primary estimand is evaluating the efficacy on disease activity of the pooled anifrolumab groups relative to placebo in subjects with active proliferative LN. This is measured by the relative difference in change from baseline to Week 52 in the 24-hour UPCR. The full analysis set, defined as subjects who are randomised and received at least 1 dose of IP (modified Intention-To-Treat), will be used, in order to reflect the effect of the initially assigned and dosed IP. Further details regarding multiplicity adjustments can be found in Section 8.6.

The analysis will be performed using a mixed model repeated measures (MMRM) fitted to log-transformed data comparing the pooled anifrolumab group with the placebo group, with fixed effects for treatment group, visit, stratification factors and log-transformed 24 hour UPCR at baseline. An interaction term for visit and treatment will also be included in the model to allow the relationship to differ across treatment groups. Note that visit will be fitted as a repeated variable in the model. Model assumptions will be checked and, if not met,

appropriate data transformations may be applied or non-parametric approaches will be considered. Details will be presented in the SAP.

The estimated treatment effect, corresponding 95% CI, and 2-sided p-value for the difference at Week 52 will be presented. The individual anifrolumab regimens will also be assessed using the same methodology. 24-hour UPCR will also be assessed at Week 104 and presented similarly with nominal 2-sided p-values.

Further, longitudinal presentations of results over time based on the same analysis, with the corresponding 95% CI, will be created.

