3 PRIMARY AND SECONDARY VARIABLES

The baseline is defined as the last measurement prior to Day 1 dose administration. If the Day 1 value is missing or is invalid, the latest assessment prior to dose administration on Day 1 will serve as baseline. If only dates (not times) are recorded then if an assessment occurs on the same day as Day 1 dose administration, it will be considered to have occurred prior to dose administration.

Baseline OCS dose will be defined as the maximum daily OCS dose taken between Day 1 and Day 7, inclusive. If no OCS are taken by the subject on Day 1 or on or before Day 7, the baseline OCS dose will be 0 mg/day.

If not stated otherwise, change from baseline will be calculated as value at the respective time point minus value at baseline.

MMF at randomisation is defined to be the Day 1 MMF dose. If the Day 1 MMF dose is missing, or no MMF is taken by the subject on Day 1, the MMF dose at randomisation will be defined as the Day 2 MMF dose.

Renal biopsies will be adjudicated, however any changes in WHO or ISN/RPS classification values due to adjudication will only be used for sensitivity analyses to evaluate the relationship between biopsy findings and baseline disease activity or response to therapy. For all other analyses and summaries, the local classification of WHO or ISN/RPS will be used.

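### The primary MMRM assumes one baseline-UPCR slope for Weeks 12 to 52; a pre-specified baseline-by-visit term would protect Week 52 precision at almost no cost

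*SAP*

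**What the plan says.** SAP 4.2.1 fits the primary MMRM to log-transformed 24-hour UPCR with "fixed effects for treatment group, visit, stratification factors and log-transformed 24-hour UPCR at baseline". The one interaction it names is treatment by visit: "An interaction term for visit and treatment will also be included in the model to allow the relationship to differ across treatment groups". Protocol 8.5.1 specifies the same structure ("An interaction term for visit and treatment will also be included in the model"). Neither document has a baseline-by-visit term.

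The covariance is unstructured ("An unstructured correlation pattern will be used to estimate the variance-covariance of the within-subject repeated measures"), with REML, Kenward-Roger degrees of freedom and a fallback list of simpler structures. On the data used, the SAP says "Separate MMRMs will be fitted to all data from baseline to Week 52 for the analyses of Week 12 to Week 52". It does not list the visit levels in that model. Protocol 5.1 schedules the 24-hour sample, after screening, at "Weeks 0, 12, 24, 36, 52, 64, 76, 88, and 104", which gives four post-baseline measurements in year 1.

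In the testing hierarchy of SAP 4.1.2, the primary endpoint is the Week 52 contrast. The model checks in SAP 4.1.6 are residual plots, histograms and Q-Q plots, and the remedies it names are transformation or non-parametric methods. The two primary sensitivity analyses (treatment policy and biopsy) change the data, not the model.

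**The concern.** A main effect for baseline says that a given difference in log UPCR at Day 1 predicts the same difference at Week 12 and at Week 52. Over a year of induction treatment, with MMF adjustment and steroid taper, that relation may weaken. The fitted slope is then a compromise. It leans towards the visit with the smallest residual variance, which in that case is Week 12, and it over-adjusts Week 52.

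What is at stake is the precision of the one contrast that is tested. The individual-regimen tests use the same method on about 50 versus 50, and the MMRM standard error also enters the futility formula in SAP 5.1. The listed checks and sensitivity analyses do not address a slope that changes over visits.

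**Working it through.** **1. The plan's own figure.** From SAP 1.3: 100 versus 50 subjects, SD 0.8, ratio 0.65, two-sided alpha 0.0499.

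- SE = 0.8 × √(1/100 + 1/50) = 0.1386; |ln 0.65| = 0.4308.
- Power = Φ(0.4308/0.1386 − 1.961) = 0.8745. The SAP states about 87%, so it reproduces. With 0.35/0.54 = 0.648 it is 0.879.

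**2. Cost of the extra term.** Four visits mean three extra parameters. With a t reference distribution, going from 145 to 142 degrees of freedom moves power from 0.8745 to 0.8744.

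**3. Closed-form loss from a common slope.** Assumptions that are not in the documents: baseline SD 0.6; baseline correlation ρ changing in equal steps over the four visits; AR(1) residual correlation of 0.7, varied from 0.5 to 0.8. The visit SD of 0.8 follows the wording of Protocol 8.2. Complete data are assumed, and the stratification factors are left out of this step.

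- Slope at visit t: b_t = ρ_t × 0.8/0.6. Residual variance: 0.64 × (1 − ρ_t²).
- Common slope: the generalised-least-squares weighted mean of the b_t.
- Gap g = common slope − b_52. Variance inflation at Week 52 = 1 + g² × 0.36/[0.64 × (1 − ρ_52²)].

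For ρ from 0.7 to 0.3 the slopes are 0.933, 0.756, 0.578 and 0.400, and the weights are 0.645, 0.052, 0.065 and 0.238. The common slope is 0.774 and g = 0.374. The inflation is 1 + 0.140 × 0.36/0.5824 = 1.087.

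| ρ, Week 12 to Week 52 | Weight on Week 12 | Gap g | Inflation (AR 0.7) | Range (AR 0.5-0.8) |
|---|---|---|---|---|
| 0.5 to 0.5 | 0.39 | 0 | 0% | 0% |
| 0.6 to 0.4 | 0.49 | 0.159 | 1.7% | 1.5-1.9% |
| 0.7 to 0.3 | 0.65 | 0.374 | 8.7% | 7-11% |
| 0.8 to 0.2 | 0.86 | 0.664 | 26% | 20-33% |

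**4. Simulation of the planned model.** This used four visits, an unstructured fit, both stratification factors and 100 versus 50, with the SD of change at Week 52 held at 0.8 (the SAP 1.3 wording). There were 700-800 runs per scenario. The entries are the Week 52 variance with the common slope divided by that with visit-specific slopes, for baseline SD 0.6 / 0.8. The dropout column assumes about 25%, depending on observed UPCR.

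| Slope, Week 12 to Week 52 | Complete data | With dropout |
|---|---|---|
| Equal | 1.00 / 1.00 | 0.99 / 0.99 |
| 0.75 to 0.55 | 1.01 / 1.03 | 1.01 / 1.05 |
| 0.85 to 0.50 | 1.04 / 1.08 | 1.07 / 1.13 |
| 0.90 to 0.30 | 1.14 / 1.36 | 1.20 / 1.46 |

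The simulated power change from adding the term was −0.6 to +1.4 points for the first three rows, against a simulation error of about 1 point, and +1.6 to +4.7 points for the last. Bias of the common-slope estimate under dropout reached −0.010 on the log scale in the third row and −0.015 in the fourth, against an effect of −0.434.

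**The case against.** The strongest reply is that nothing in the documents shows that the slope changes. They give no visit-specific slopes or correlations and no baseline SD. With equal slopes the planned model loses nothing and is marginally the more efficient. That stands: the loss is conditional, and a reader who infers that Week 52 precision is known to be lost goes beyond the documents.

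Four other stronger readings are also unsupported:

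- **Planned power is missed.** In the 0.7 to 0.3 case the common-slope residual variance is 0.5824 + 0.374² × 0.36 = 0.633, an SD of 0.795, about the planned 0.8. What is forgone is a gain. Only the extreme 0.8 to 0.2 pattern takes the SD clearly above plan (√(0.6144 × 1.259) = 0.88), and no document says that it applies.
- **The estimate is materially biased.** In the 0.7 to 0.3 case a one-SE chance imbalance in baseline (0.6 × √0.03 = 0.104) shifts Week 52 by 0.374 × 0.104 = 0.039. Over randomisations this averages to zero: it is the same variance inflation seen from another side. Stratification on UPCR limits such imbalance, and the simulated bias with dropout was small.
- **Retests will break the unstructured fit.** A retest 14 days after Week 12 or Week 24 falls on Day 99 or Day 183, the first day of the Week 16 or Week 28 window. But SAP 4.2.1 excludes data after the last dose in subjects who stop, which removes many confirmed retests. No convergence failure has been shown, and a fallback sequence is specified.
- **The stratification-sample UPCR should be a second continuous covariate.** It already enters as a stratum beside the Day 1 baseline, and no gain from adding it has been established here.

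The two documents also attach the SD of 0.8 to different quantities: values in Protocol 8.2, change from baseline in SAP 1.3. With visit SD 0.8, baseline SD 0.6 and correlation 0.3, the SD of change would be √(0.64 + 0.36 − 2 × 0.3 × 0.48) = 0.84, so the closed-form percentages do not transfer exactly to the SAP's wording.

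**Conclusion.** The point holds as a conditional efficiency recommendation. The primary model imposes a constant baseline slope that the analysis does not need, and nothing in the plan would detect or repair a departure from it. Under the assumptions above, the Week 52 variance inflation is 0% with equal slopes, about 2% for a mild fall in correlation, 7-11% for a fall from 0.7 to 0.3, and 20% or more for 0.8 to 0.2, with somewhat more under dropout. The documents cannot say which case applies. The planned analysis is valid. The argument for change rests on asymmetry: the worst cost of adding the term is about 1% of variance, whereas the cost of omitting it can reach double digits. Minor.

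**What to change.** Before unblinding, add a log-baseline 24-hour UPCR by visit term to the primary MMRM in SAP 4.2.1. State that the visit levels in the Week 52 model are the scheduled 24-hour UPCR visits: Weeks 12, 24, 36 and 52. Record the departure from Protocol 8.5.1 in SAP section 6. The treatment-policy and biopsy sensitivity analyses and the individual-regimen comparisons should carry the same term.

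The cost is a wording change to the primary model, 3 degrees of freedom, about 0.01 power point, and up to about 1% more variance if the slopes turn out equal. No change to data collection, sample size or the testing hierarchy is needed.

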4.2.2 Analysis of the secondary variable

As a secondary endpoint, a composite endpoint is used to evaluate the effect of anifrolumab on renal response. For this analysis the estimand of interest is the difference in change from baseline at Week 52 in renal response between anifrolumab and placebo, to reflect the effect of the initially assigned IP (full analysis set). This estimand answers a clinically relevant question comparing the number of subjects able to both tolerate therapy sufficiently to remain on treatment to a given point in time and to achieve adequate response without further medication being required. Any missing data will be imputed as defined in Section 4.1.4.

The proportion of subjects achieving CRR in the anifrolumab pooled group will be compared with the placebo group using a CMH approach (Stokes ME, 2012) stratified by:

- Results of IFN test at screening using a 4-gene type I IFN test (IFN test-high versus test-low)
- 24-hour UPCR ≤ 3.0 mg/mg versus >3.0 mg/mg at screening (within 14 days prior to the expected date of randomisation). Without the results of the second (stratification) sample, subjects cannot be randomised. Turn-around time for results from central laboratory is up to 7 days. On rare occasion an extension of 30-day screening window is allowed if re-collection of the sample is necessary or the results needed for randomisation are delayed.

The individual anifrolumab regimens will also be assessed but not as part of the secondary analysis. The analysis can be described as follows:

- There are n_{ij} subjects in each stratum, where i is the stratum, and j is the treatment group. The number of responders is x_{ij} . The proportion of responders is denoted as $p_{ij} = x_{ij} / n_{ij}$.
 Strata with low counts will be pooled with adjacent strata. If a sub-stratum within the IFN-low stratum has less than 16 subjects (in the pooled treatment group, i.e. placebo pooled with the respective anifrolumab group that is tested), then the two IFN-low sub-strata will be pooled together. If a sub-stratum within the IFN-high stratum has less than 16 subjects (in the pooled treatment group), then the two IFN-high sub-strata will be pooled together. If the two IFN-low sub-strata are pooled together and the two IFN-high sub-strata are pooled together, and any of these strata has less than 16 subjects (in the pooled treatment group) then all strata will be pooled together.
- For each stratum, the difference in proportion of subjects achieving CRR is calculated as $d_i = p_{iA} - p_{iP}$, where A and P denote the different treatment groups (anifrolumab and placebo, respectively).
- Weights for each stratum, w_i , are calculated as $n_{iP} \times n_{iA} / (n_{iA} + n_{iP})$. The weighted difference is calculated as

$$WD = \frac{\sum w_i d_i}{\sum w_i}$$

- The SE of the weighted difference under the null hypothesis is given by

$$SE = \sqrt{\frac{\sum [w_i^2 \text{Var}(d_i)]}{(\sum w_i)^2}}$$

$$\text{Var}(d_i) = \frac{p_i(1 - p_i)n_i}{w_i(n_i - 1)}$$

$$p_i = \frac{x_i}{n_i} = \frac{x_{iA} + x_{iP}}{n_{iA} + n_{iP}}$$

- For deriving the CI for the weighted difference in proportions, a correction will be applied to the variance, providing a CI with more accurate coverage. This will be applied to all strata and is derived as below. The 95% confidence interval can be generated using the weighted difference $\pm Z_{0.975} \times SE$.

$$\text{Var}(d_i) = \frac{p_{iA}^*(1 - p_{iA}^*)}{n_{iA}} + \frac{p_{iP}^*(1 - p_{iP}^*)}{n_{iP}}$$

$$p_{ij}^* = \frac{x_{ij} + 2}{n_{ij} + 4}$$

- The 95% confidence interval for the weighted proportion ($\sum_i w_i p_{ij}/w$) in a treatment group j can be generated using a normal approximation and independence between strata, where p_{ij}^* are used as above

$$s_{ij}^2 = Var(p_{ij}) = p_{ij}^*(1 - p_{ij}^*)/n_{ij}$$

$$s_j^2 = \sum_i w_i^2 s_{ij}^2/w^2$$

$$w = \sum_i w_i$$

- The value of the test statistic is calculated as $\frac{WD}{SE}$. The p-value from the two-sided test of no difference in treatment groups is calculated as $2 \left(1 - Prob \left(\left| \frac{WD}{SE} \right| \right) \right)$, where $Prob(.)$ is the distribution function of the standard normal distribution.

The estimated treatment effect (the difference in response rate for each anifrolumab regimen versus placebo) and corresponding 95% CI for the difference at Week 52 and Week 104 will be presented. In addition, the response rate and the corresponding 95% CI within each treatment group will be presented.

The following sensitivity analyses will also be performed to assess the robustness of this secondary outcome variable at Week 52 and Week 104:

- A tipping point analysis to examine the impact of missing data, including the impact of non-responder imputation due to permanent discontinuation of IP. The analysis for each treatment group, and the pooled anifrolumab group, will only be statistically interpreted if the nominal p-value from the analysis of CRR detailed above, for the respective comparison with placebo at the specified visit, is <0.05 (in favour of anifrolumab). This analysis will vary the assumptions about outcomes among the subsets of subjects on the treatment arms who permanently discontinued IP early, and can be described as:
 - The proportions of responders will be analysed using a Pearson's chi-squared test, i.e., disregarding the stratification factors that are used in the main analysis (CMH).
 - Subjects who permanently discontinued IP early having not received restricted medications prior to discontinuation are by definition imputed as non-responders. For this sensitivity analysis, these subjects will be considered as having had the potential of being responders if they continued into the study until Week 52.
 - At each step of the analysis one of these subjects switches from non-responder to responder, and the Pearson's chi-squared test is re-run. The results (statistical significance) will be presented for each anifrolumab treatment arm as well as the pooled anifrolumab group in a grid where the x-axis and the

y-axis represent the number of subjects that have had their values imputed as non-response values and are assumed as responders for the placebo arm and the active arm respectively. The region where the conclusion changes, will be considered as the tipping point.

- The grid will be divided into three regions, limited in the top by the expected number of subjects that have had their values imputed as non-response values in the active arm which would have been responders if not permanently discontinued IP early (based on the active response rate in the observed cases):
 - Likely – its right limit is the expected number of subjects that have had their values imputed as non-response values in the placebo arm which would have been responders if not permanently discontinued IP early (based on the placebo response rate in the observed cases);
 - Uncertain – its right limit is the expected number of subjects that have had their values imputed as non-response values in the placebo arm which would have been responders if not permanently discontinued IP early (based on the active response rate in the observed cases);
 - Unlikely – it is the region to the right of the uncertain region.
- Biopsy sensitivity analysis: Based on the main analysis it excludes any subjects whose adjudicated kidney biopsy results show them to be ineligible for study entry.

Subgroup analyses will be performed as described in Section 4.3.

Longitudinal presentations of results over time (i.e. for each post-baseline visit up to Week 104 where CRR based on 24-hour UPCR can be derived) based on the same analysis, with the corresponding 95% CI, will be created. Bar plots showing the proportion of subjects who are responders/non-responders for CRR at Week 24 and Week 52 by treatment group (including CIs and number of subjects included in the analysis) will be provided by 24-hour UPCR at screening (≤ 3 mg/mg and > 3 mg/mg). Additionally, the individual components of CRR will be summarised over time by treatment group.

The proportion of subjects achieving CRR based on 24-hour UPCR at Week 52 and at Week 104 will also be presented in a summary table alongside the proportion of subjects achieving CRR based on spot UPCR at Week 52 and at Week 104 together with a summary of the individual components.

In addition, the time to achieve CRR by treatment group will be presented in a Kaplan-Meier plot including the number of subjects at risk at each visit.

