4.2.3.3 Oral corticosteroid management

The exploratory endpoint used to evaluate the effect of the anifrolumab regimens versus placebo on the ability to achieve a sustained reduction of OCS dose is the difference in proportions of subjects able to taper OCS to ≤ 7.5 mg/day prednisone-equivalent by Week 24 and maintain this dose through Week 52. The effect of the anifrolumab regimens versus placebo will also be evaluated on the ability to achieve a sustained reduction of OCS dose using the difference in proportions of subjects able to taper OCS to ≤ 5.0 mg/day prednisone-equivalent by Week 80 and maintain this dose through Week 104.

The same CMH approach as described in Section 4.2.2 will be used to estimate the treatment differences between the anifrolumab regimens and placebo at Week 52 and at Week 104. Any missing data will be imputed as defined in Section 4.1.4.

Subgroup analyses will be performed as described in Section 4.3.

Reduction of OCS dose will also be assessed at Week 24 by examining the proportions of subjects able to taper OCS to ≤ 7.5 mg/day prednisone-equivalent by Week 24, using the same analysis approach. Reduction of OCS dose will also be assessed at Week 80 by examining the proportions of subjects able to taper OCS to ≤ 5.0 mg/day prednisone-equivalent by Week 80, using the same analysis approach.

In order to examine the impact of missing data, a tipping point analysis as described in Section 4.2.2 will also be performed for the sustained reduction of OCS dose at Week 52 and Week 104. The analysis for each treatment group, and the pooled anifrolumab group, will only be statistically interpreted if the nominal p-value from the main analysis of sustained reduction of OCS dose detailed above, for the respective comparison with placebo at the specified visit, is <0.05 (in favour of anifrolumab).

Daily OCS doses and changes from baseline will be presented by descriptive statistics by visit for all subjects.

Additionally, the daily OCS dose will be displayed graphically by a longitudinal plot presenting the means and corresponding SDs. The number of subjects will also be included in the graph.

Shift plots (scatter plot) for the daily OCS dose presenting baseline values versus Week 24 values, baseline values versus Week 52 values and Week 52 values versus Week 104 values will also be provided. A diagonal line indicating no change will be included in this shift plot.

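### The CRR tipping-point grid is read only if the stratified CMH test is significant, yet its cells use an unstratified Pearson test, so a moderately significant result can start out tipped

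*SAP*

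**What the plan says.** SAP section 4.2.2 states that CRR in the pooled anifrolumab group "will be compared with the placebo group using a CMH approach", with IFN test and screening 24-hour UPCR as strata. It gives the weights, the null variance and a collapsing rule that begins "If a sub-stratum within the IFN-low stratum has less than 16 subjects".

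The same section then sets out the tipping-point analysis:

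- **Condition for reading it.** It "will only be statistically interpreted if the nominal p-value from the analysis of CRR detailed above" is below 0.05 in favour of anifrolumab. That p-value is the stratified CMH one.
- **Test in the grid.** Pearson's chi-squared test, "disregarding the stratification factors that are used in the main analysis (CMH".
- **Stepping.** "At each step of the analysis one of these subjects switches from non-responder to responder, and the Pearson's chi-squared test is re-run".
- **Definition.** "The region where the conclusion changes, will be considered as the tipping point".

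No reason is given for the change of test. Nothing requires the Pearson result with no switches to agree with the CMH result, and nothing says how to read the grid if it does not. SAP section 4.2.3.3 carries the method over to sustained OCS reduction: "a tipping point analysis as described in Section 4.2.2 will also be performed".

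**The concern.** A tipping-point analysis asks how far the assumption about early discontinuers must move before the conclusion changes, so everything else should stay fixed. Here the test changes as well, before any subject is switched. When a stratification factor predicts the outcome, the unstratified test has a larger standard error for the same observed difference. The cell with no switches, (0,0), then need not reproduce the main analysis, and the boundary in the rest of the grid is displaced too.

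What is at stake is how a secondary-endpoint sensitivity analysis is read. Followed as written, the plan could display a result that met its own condition as tipped although no imputation had been altered.

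**Working it through.** **Inputs from the SAP.** 50 subjects per arm, hence 100 pooled versus 50 placebo (section 1.3); the CMH formula and collapsing rule (section 4.2.2). The significance level for grid cells is not stated; two-sided 5% is taken. CRR rates by stratum are not in the documents and are assumed throughout.

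**The plan's own figure.** There is no CRR power to reproduce. The power of about 87% for the primary endpoint does reproduce: |ln 0.65| / (0.8 × √(1/100 + 1/50)) = 0.4308/0.1386 = 3.109; 3.109 − 1.961 = 1.148; Φ(1.148) = 0.87. This confirms the 100 versus 50 layout.

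**Formulas.**

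- CMH (SAP): w = nA·nP/(nA+nP); Var(d) = p(1−p)n/[w(n−1)]; SE = √Σw²Var(d) / Σw; z = WD/SE.
- Pearson: z = d/√[p(1−p)(1/nA + 1/nP)], with all strata combined.

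**Worked table at (0,0), two equal UPCR strata.**

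| UPCR stratum | Anifrolumab | Placebo | d | Combined p | Var(d) |
|---|---|---|---|---|---|
| ≤3 | 30/50 | 11/25 | 0.16 | 41/75 = 0.547 | 0.01507 |
| >3 | 12/50 | 2/25 | 0.16 | 14/75 = 0.187 | 0.00923 |
| All | 42/100 | 13/50 | 0.16 | 55/150 = 0.367 | |

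- CMH: w = 50×25/75 = 16.67 in each stratum, so SE = √(0.01507 + 0.00923)/2 = 0.0779; z = 0.16/0.0779 = 2.053; **p = 0.0401**. The condition is met.
- Pearson: SE = √(0.2322 × 0.03) = 0.0835; z = 1.917; **p = 0.0552**. The grid starts non-significant.

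The difference is 0.16 in both; only the standard error changes.

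**Away from the origin.** Take a stronger table: anifrolumab 34/50 and 16/50, the same placebo counts, CMH p = 0.0027. Switch four placebo subjects to responder, so that the totals are 50/100 versus 17/50.

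- Pearson: z = 0.16/√(0.2472 × 0.03) = 1.858, p = 0.063.
- CMH, all four in the ≤3 stratum (15/25 and 2/25): SE = 0.0788, z = 2.029, p = 0.042.
- CMH, all four in the >3 stratum (11/25 and 6/25): SE = 0.0825, z = 1.940, p = 0.052.

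Pearson calls this cell tipped. Under CMH the answer depends on which stratum the switched subjects came from.

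**How often the origin is discordant** (CMH p<0.05 in favour of anifrolumab, Pearson p≥0.05). Simulations of 100 versus 50 with two equal UPCR strata; CRR is placebo/anifrolumab:

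| UPCR ≤3 | UPCR >3 | Share of trials with CMH p<0.05 |
|---|---|---|
| 50%/68% | 10%/24% | 14.5% |
| 50%/72% | 10%/28% | 8.5% |
| 42%/60% | 18%/34% | 2.9% |

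A wider set adds the IFN factor (5% or 20% IFN-low) and the collapsing rule, with odds ratios of 1.5 to 2.5. Results by placebo CRR in the two UPCR strata, pooled versus placebo: 0.4–3% (30%/30%), 2–7% (40%/20%), 7–18% (50%/15%), 21–38% (60%/10%). For a single regimen the overall range is about 0.5–43%.

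**Which results are affected.** In the three tabulated scenarios the median CMH p among discordant trials is 0.040, 0.040 and 0.047, and no trial with CMH p<0.01 was discordant. In a more extreme case (60%/75% and 10%/20%), 0.2% of trials with CMH p<0.01 were discordant.

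**Is the stratum likely to predict CRR?** CRR requires an absolute UPCR ≤0.7. Apply the design ratios of 0.54 and 0.35 and the log-SD of 0.8 to assumed typical baselines of 2 and 5. The chance of meeting the UPCR component is then 29% versus 5% on placebo (for example Φ[ln(0.7/1.08)/0.8] = 0.29) and 50% versus 13% on anifrolumab. Origin discordance is about 12% of qualifying trials. Other assumed baseline pairs give 2% (2.5 and 4) to 29% (1.5 and 6).

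**The case against.** The strongest reply is that this is a disclosed, pre-specified sensitivity analysis. A grid cell fixes only how many subjects are switched, which is enough for Pearson's test but not for CMH; that is a practical reason for the simpler test, and it stands. Where strata are prognostic, Pearson mostly errs towards understating robustness. The reverse disagreement occurred in about 1.6% of simulated trials or fewer, and those fail the CMH condition and are not interpreted. A non-significant origin would be visible in the grid. If all strata collapse into one, the CMH z² is (n−1)/n times the Pearson chi-squared, so this problem cannot arise. These points limit the concern but do not reconcile the two tests.

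Two stronger readings are tempting.

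- A reader might infer that a robust CRR result could be shown as tipped at zero switches. The figures do not support that: discordance at the origin is confined almost entirely to CMH p-values between about 0.01 and 0.05.
- A reader might infer that the grid says nothing about missing data. It still shows how the conclusion moves as discontinuers are switched, with its likely, uncertain and unlikely regions; the boundary is displaced, not meaningless.

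**Conclusion.** The concern holds in a limited form. The SAP conditions interpretation on one test and defines the tipping point by another, without reconciling them, so the grid mixes the loss of stratification with the missing-data assumption. A result with CMH p moderately below 0.05 can appear tipped with nothing imputed differently.

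The frequency is about 3% to 15% of qualifying trials in the three main scenarios and 0.4% to 38% over the wider range for pooled versus placebo. It rests on assumed CRR rates by stratum and depends mainly on how strongly the UPCR stratum predicts CRR, which the documents do not quantify.

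The confirmatory CRR test, its estimate and the type I error are untouched. For sustained OCS reduction the same mismatch of tests is on the page, but no size of effect has been shown. The UPCR argument does not carry over directly, and that endpoint is restricted to subjects with baseline OCS of at least 20 mg/day (SAP section 3.3.7), a smaller set in which strata are more likely to collapse. This is a worthwhile improvement, not a flaw in the main analysis.

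**What to change.** In SAP section 4.2.2, compute the SAP's own CMH statistic in every grid cell, with the same strata and collapsing rule as the main analysis. Cell (0,0) then equals the main analysis by construction, and discordance at the origin is zero.

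Because a cell fixes only the number switched, use the actual strata of the eligible discontinuers and label each cell as significant under all, some or no stratum allocations, that is, best and worst case. This is preferable to averaging CMH p-values over random draws, since an average of p-values is not a calibrated p-value. The Pearson grid can stay as a supplementary display.

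For consistency, apply the same test-matching rule to the OCS tipping-point analysis in section 4.2.3.3.

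The cost is a little more programming, since the randomisation strata are already recorded. The drawback is that some cells will be labelled as depending on allocation.
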